2.4 Determination of sample size

No formal statistical sample size calculation has been performed for the dose escalation modules in study ONC001.

The number of participants likely to be enrolled in Part B depends on how many dose levels are needed to define the RP2D-T for combination therapy. In Part B, up to 27 eligible participants will be enrolled. It is expected that up to 3 dose levels of UCB6114 will be explored in combination with the TFD/TPI dosing regimen, respectively. However, additional dose levels may be added based on emerging data and recommendations of the SMC.

Between 3 and 9 participants are expected to be enrolled at each dose level of UCB6114 depending on the observed toxicity/observation of DLTs. An administrative decision to stop enrolling into Part B may be made by the Sponsor at any time. “Dose level” refers to a particular UCB6114 dose, that can be given to one or more cohorts, not necessarily consecutively.

The operating characteristics of the mTPI design were evaluated using a simulation approach under four scenarios (see Table 2-1) and based on no DLTs observed in the first 2 cohorts in Part A monotherapy treatment (UCB6114 100mg and 250mg). The results of this evaluation can be seen in Table 2-2.

Table 2-1: Scenarios used for evaluating the operating characteristics of the mTPI design. Orange cells indicate the correct decision assuming a maximum tolerated toxicity of 25% (equivalence limits 20%, 30%)

UCB6114 Dose	Probability of a DLT			
	Scenario 1	Scenario 2	Scenario 3	Scenario 4
Dose 1 (500 mg)	0.05	0.05	0.15	0.25
Dose 2 (1000 mg)	0.05	0.15	0.25	0.35
Dose 3 (2000 mg)	0.05	0.25	0.35	0.50

Table 2–2: Evaluation of the operating characteristics of the mTPI design with a target maximum tolerated toxicity of 25%, using 5000 simulated trials for each scenario. Orange cells indicate the correct decision.

Final UCB6114 Dose Selected	Scenario 1	Scenario 2	Scenario 3	Scenario 4
	% of Simulations (Number of Simulations)			
Dose 1 (500 mg)	3.9% (196)	5.2% (262)	31.6% (1580)	53.3% (2666)
Dose 2 (1000 mg)	3.9% (195)	35.1% (1755)	40% (1999)	26.7% (1337)
Dose 3 (2000 mg)	91.4% (4571)	58.9% (2947)	21.6% (1080)	3.8% (191)
Overly Toxic at First Cohort	0.8% (38)	0.7% (36)	6.7% (336)	15.2% (758)
Overly Toxic after First Cohort	0	0	0.1% (5)	1% (48)

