3. DATA ANALYSIS CONSIDERATIONS

3.1 General presentation of summaries and analyses

All TFLs will be produced by ICON PLC using SAS® Version 9.4 or higher (SAS Institute, Cary, North Carolina, USA). ICON PLC will also produce the analysis datasets which will adhere to the Clinical Data Interchange Standards Consortium (CDISC) guidance documents for Analysis Data Model (ADaM) and follow the Sponsor's interpretation. General statistical and reporting conventions will follow the current UCB Global Conventions Document Version 1.1.

Data will be summarized by UCB6114 dose level (treatment group), visit and timepoint, as applicable. All relevant reported and derived data will be listed and will be presented by treatment group, study participant and visit, as applicable.

Categorical variables will be summarized using frequency counts and percentages. Unless otherwise stated, the denominator for the percentages will be based on the number of participants in the respective analysis set, treatment group, visit and timepoint (as applicable) with non-missing data.

When reporting frequency counts and percentages, the following rules apply:

- For categories where all participants fulfill certain criteria, the percentage value will be displayed as 100;
- For categories where zero participants fulfill certain criteria, there will be no percentage displayed;
- All other percentage displays will use 1 decimal place.

Summary statistics will be presented for continuous variables including number of participants (n), arithmetic mean, standard deviation, median, minimum and maximum. 95% confidence

intervals (CIs) for the arithmetic mean may also be included depending on the variable and where stated in the SAP. Geometric mean (geoMean), geometric coefficient of variation (geoCV) and 95% CI for the geoMean will also be presented in the summaries of UCB6114 concentration data. In all relevant outputs the 95% confidence limits will be restricted to the possible values that the variable can take.

When reporting descriptive statistics for data other than UCB6114 concentration data, the following rules will apply:

- n will be an integer;

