- Mean (arithmetic and geometric), standard deviation, median and quartiles will use 1 decimal place more, or 1 significant figure more – depending on the reporting format of the original data – than the original data. Original data may be data as reported directly onto the eCRF or summary data based on data reported onto the eCRF (e.g. mean of triplicates or percentage change from Baseline);
- Confidence intervals will be presented to the same number of decimal places as the value around which the CI is constructed;
- Minimum and maximum will be reported using the same number of decimal places or significant figures as the original value;
- A minimum of 3 values are required to calculate summary statistics. If only 2 values are available, then these should be presented as the minimum and maximum with other summary statistics reported as missing ("– ");
- If no participants have data at a given timepoint, then only n=0 will be presented;
- Percentage change from Baseline values will be calculated and displayed to 1 decimal place in the listings. In the summaries, where applicable, the mean, standard deviation and median percentage change from Baseline values will be presented to 2 decimal places and the minimum and maximum values presented to 1 decimal place.

[figure not shown]
When reporting individual UCB6114 concentration data in listings and figures, and presenting summary statistics in tables, the following rules will apply:

- UCB6114 concentration data should be reported in the listings to the same level of precision as received from the bioanalytical laboratory;
- Missing data should be reported as 'NV' (no value) in the listings;
- Concentrations below the lower limit of quantification (LLOQ) should be reported as BLQ (below the limit of quantification) in the listings;
- BLQ values prior to C_{max} should be set to 0 for purposes of plotting a figure (to capture lag-time);
- Actual sampling times will be used in the spaghetti plots of individual PK concentrations over time, and nominal sampling times will be used in the summaries of geoMean concentrations over time;
- UCB6114 concentration data should be plotted on both linear and semi-logarithmic scales;

- To calculate summary statistics, BLQ values should be set to half the LLOQ value and missing values should be excluded;

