9.2 Pharmacodynamics

The following exploratory PD and biomarker endpoints will be obtained from blood and urine samples which will be analyzed at a number of external laboratory vendors:

- Serum markers of bone turnover;
- Urinary markers of bone turnover;
- cGremlin-1;
- Genetic analysis;
- ctDNA.

The impact of UCB6114 on bone turnover will be explored using the serum and urinary markers provided by the analytical laboratory. These markers will be listed for the SS and summarized descriptively over time for the PDS by dose level (treatment group), as described for the clinical laboratory parameters in [Section 8.3](#). For each marker of bone turnover, the mean (\pm standard deviation) value and the mean (\pm standard deviation) change from Baseline value will be plotted over scheduled visit with treatment group overlaid on the same plot.

cGremlin-1 will be reported as concentration in blood by nominal (scheduled) assessment and dose level. Concentrations of cGremlin-1 will be listed for the SS and summarized for the PDS using descriptive statistics by dose level (treatment group) and nominal (scheduled) sampling timepoints (n, arithmetic mean, standard deviation, median, minimum, maximum, geoMean, geoCV and 95% CI for the geoMean [assuming lognormally distributed data]). Changes from Baseline will also be summarized. Individual study participant cGremlin-1 concentration-time profiles will be displayed graphically in spaghetti plots and geoMean cGremlin-1 concentration and 95% CI will be plotted at each nominal (scheduled) timepoint with treatment group overlaid on the same plot.

Genetic analysis and the analysis of the test results from the blood samples taken for ctDNA will be performed and reported separately outside of the CSR.

Hematoxylin and eosin (H & E) staining and immunohistochemistry (IHC) will be used to analyze any available historical tissue biopsy samples obtained prior to a participant's entry into the study (e.g. at the time of diagnosis).

Test results from the H & E staining and for target genes, phosphatase and tensin homolog (PTEN), Ki67 (cellular marker for proliferation in tumors), Gremlin-1, mothers against decapentaplegic homolog 4 (SMAD4) and fibroblast activation protein (FAP) will be listed by variable and sample analyzed (multiple tissue samples from a tumor biopsy may have been analyzed for a participant) for the SS. No summaries of these data will be generated due to the

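### Change from Baseline in cGremlin-1 has no stated scale and defaults to arithmetic summaries without a CI, although the level is treated as lognormal; a paired ratio to Baseline would suit 3 to 9 participants per dose better

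*SAP*

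**What the plan says.** Section 9.2 (Pharmacodynamics) of the Part B SAP lists the statistics for cGremlin-1 concentration by dose level and nominal timepoint. They are the usual arithmetic ones plus geoMean, "geoCV and 95% CI for the geoMean [assuming lognormally distributed data". The next sentence is "Changes from Baseline will also be summarized". It does not say whether the change is a difference, a percentage or a ratio, and it names no statistics. Section 9.2 of the Part C SAP uses the same wording.

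The general rules in Section 3.1 fill the gap. For continuous variables, "Summary statistics will be presented for continuous variables including number of participants (n), arithmetic mean, standard deviation, median, minimum and maximum". CIs for an arithmetic mean are given only where the SAP states them, and Section 9.2 states none for the change. Geometric statistics are extended to one variable: "95% CI for the geoMean will also be presented in the summaries of UCB6114 concentration data". There is also a display rule for percentage change, "In the summaries, where applicable, the mean, standard deviation and median percentage change from Baseline values will be presented to 2 decimal places", but it is not assigned to cGremlin-1.

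On group size, Section 2.4 says "Between 3 and 9 participants are expected to be enrolled at each dose level of UCB6114".

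Two further provisions matter for the fix. Table 3-1 makes the Cycle 1 Day 1 predose sample the cGremlin-1 Baseline. Section 4.2.1, whose heading covers both pharmacokinetics and pharmacodynamics, assumes a value of zero at that same timepoint.

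**The concern.** The plan adopts a log scale for the level and then does not carry it to the change, which is the summary that isolates each participant's own response. If the effect is multiplicative, the absolute change equals Baseline x (ratio - 1). A group mean of such changes mixes how high participants started with how they responded. In groups of 3 to 9, two dose levels with the same fold effect can then show different mean changes because their Baselines differ.

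PD biomarker data are one element of the information from which Section 2.3 says the recommended Phase 2 dose will be chosen, and Section 4.5 has the Safety Monitoring Committee review them. A by-dose summary that separates response from Baseline level, with an interval, would be more useful there than a mean difference without one.

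**Working it through.** The SAPs state no SD, geoCV, power or precision for cGremlin-1, so there is no planned figure to reproduce. The check asks how the two summaries behave under stated assumptions.

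**Inputs from the SAP:** lognormal level (Section 9.2); n between 3 and 9 per dose (Section 2.4), with n=6 used as the middle.

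**Assumptions, not in the SAP:** Baseline B is lognormal with geoCV c_B = 50% or 100%. The individual ratio R is lognormal, independent of B, with geometric mean 2 and geoCV c_R = 30% or 50%.

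**Mean absolute change.** D = B(R - 1).
- E(R) = 2√(1 + c_R²) and SD(R) = c_R E(R).
- CV²(D) = (1 + c_B²)(1 + [SD(R)/(E(R) - 1)]²) - 1. Divide CV(D) by √n for the mean.
- c_B=0.5, c_R=0.3: E(R)=2.088, SD(R)=0.626, (0.626/1.088)²=0.331. CV²(D)=1.25 x 1.331 - 1=0.664, so CV(D)=0.815, and 0.815/√6=0.33.
- c_B=1, c_R=0.5: E(R)=2.236, SD(R)=1.118, (1.118/1.236)²=0.818. CV²(D)=2 x 1.818 - 1=2.636, so CV(D)=1.624, and 1.624/√6=0.66.

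**Geometric mean ratio (GMR).** Let v = ln(1 + c_R²)/n.
- E(GMR)=2exp(v/2) and SD(GMR)=E(GMR)√(exp(v) - 1).
- For a like-for-like comparison, divide by the effect, E(GMR) - 1, not by the ratio itself.
- c_R=0.3: v=0.0144, E=2.014, SD=0.242, 0.242/1.014=0.24.
- c_R=0.5: v=0.0372, E=2.037, SD=0.397, 0.397/1.037=0.38.

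**Results, n=6, 2-fold rise.** The formulas agree with simulation (100,000 groups per setting) to within 1 percentage point. The last column is the simulated median share.

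| Baseline geoCV | Ratio geoCV | CV, mean change | CV, GMR relative to effect | Highest-Baseline participant's share of total change |
|---|---|---|---|---|
| 50% | 30% | 33% | 24% | 26% |
| 50% | 50% | 46% | 38% | 24% |
| 100% | 30% | 53% | 24% | 35% |
| 100% | 50% | 66% | 38% | 33% |

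The equal share is 1/6 = 17%. The GMR column does not move with Baseline spread, whereas the mean-change column does.

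**Counter-cases.** If change is additive and unrelated to Baseline, the highest-Baseline participant's share is the equal one (33%, 17% and 11% at n=3, 6 and 9). With Baseline geoCV 30%, within-participant CV 40% and a doubling, the excess also disappears: 27% at n=3 and 5% at n=9.

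**Constructed example of disagreement.** Baselines are 1, 1.2 and 8; the first two double and the third falls by 40%. The changes are +1, +1.2 and -3.2, so the mean is -1.0/3 = -0.33 and the median is +1.0. The GMR is (2 x 2 x 0.6)^(1/3) = 1.34. The mean and the ratio point in opposite directions.

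**The case against.** Several points on the other side stand.

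- **The point estimate is nearly there already.** Section 9.2 requires the geoMean at every nominal timepoint, including the Baseline sample. When the same participants contribute at both visits, the quotient of the two geoMeans is the GMR. What is missing is a paired CI and geoCV, and correct handling when some participants have only one of the two values. The individual profiles and the plot of geoMean with 95% CI also show the data on a sensible scale.
- **A lognormal level does not prove a multiplicative effect.** The SAP makes the assumption to form a CI for the level. A proportional drug effect is plausible but nowhere stated.
- **The arithmetic difference is inferred from the default.** Percentage change is not excluded, and the table mocks are not available here. Either reading still leaves Section 9.2 without a stated scale.
- **The median is reported as well.** It resists one extreme participant. It is still an absolute difference that depends on Baseline, and its sampling CV was about the same as the mean's in the settings run.

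A reader might go further and infer that the mean change is driven by whoever started highest. The documents do not support that. It needs proportional change and a wide Baseline spread, and even then the share at n=6 is 24-35%, not a majority. The largest single change makes up about 34-46% of the total, but that figure mostly reflects response noise and the taking of a maximum: it is already 29-37% with no Baseline variation at all. A reader might also set 33-66% against the GMR's raw CV of 12-19%. That divides one SD by the effect and the other by the whole ratio, and so overstates the contrast.

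**Conclusion.** The point holds as a minor specification gap with a better alternative at hand. The level is treated as lognormal, the change has no stated scale, and the default gives arithmetic summaries of the difference without a CI. Under a proportional effect the paired ratio is more precise. At n=6 and a 2-fold rise the gain is modest when Baseline spread is lower (33% against 24%, or 46% against 38%) and larger when it is wide (53% against 24%, or 66% against 38%). High-Baseline participants then carry about 1.5 to 2 times their equal share. All of these sizes rest on assumed geoCVs and on proportionality, which the SAPs neither give nor rule out.

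A reader might infer that dose selection is compromised. That does not follow. The endpoint is exploratory and descriptive, no threshold or decision rule uses the change in cGremlin-1, and PD data are only one part of the totality considered.

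**What to change.** In Section 9.2 of both SAPs:

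1. State that change in cGremlin-1 is summarized as the ratio to Baseline: geometric mean ratio, geoCV and 95% CI from log(post/Baseline), by dose level and nominal timepoint, in participants with both values.
2. Keep the absolute change as supportive.
3. State in Section 4.2.1 that the zero-predose rule applies to UCB6114 concentration only. The cGremlin-1 Baseline is that same sample (Table 3-1); if it were set to zero, the log ratio would be undefined.

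The cost is SAP wording, one derived variable and one extra set of table rows. No new data are needed.

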Variable No.	FAP Derived Variable	Description and Calculation
1 ^[a]	Total Analyzed Tumor Area (um ²)	This is the total tumor area (um ²) across the CN tumor region and the IM region and will be calculated as the sum of the areas of the CN tumor region (um ²) and the IM region (um ²) where a non-missing numeric test result is available for both the area of the CN tumor region and the area of the IM region. Note that, in cases where no IM region is defined, the area of the IM region will be recorded as 0 or 'NOT APPLICABLE', or may be missing. If the area of the IM region is recorded as 'NOT APPLICABLE' or is missing, then 0 will be assumed in this calculation and the total analyzed tumor area will be equal to the area of the CN tumor region.

Variable No.	FAP Derived Variable	Description and Calculation
		This variable will be missing if both the areas of the CN tumor region and IM region are missing, or if one or both are 'NOT EVALUABLE' or 'NOT DIAGNOSTIC'.
2	Measured Area of Weakly Stained FAP in the CN Tumor Region (μm^2)	
This is the back-calculated area of weakly stained FAP in the CN tumor region (weak positive) and will be calculated by multiplying the area of the CN tumor region (μm^2) and the relative area of weakly stained FAP in the CN tumor region (%) where a non-missing numeric test result is available for both the area of the CN tumor region and the relative area of weakly stained FAP in the CN tumor region.
 
This variable will be set to 0 if one or both are missing, 'NOT EVALUABLE' or 'NOT DIAGNOSTIC'.

3	Measured Area of Moderately Stained FAP in the CN Tumor Region (μm^2)	
This is the back-calculated area of moderately stained FAP in the CN tumor region (moderate positive) and will be calculated by multiplying the area of the CN tumor region (μm^2) and the relative area of moderately stained FAP in the CN tumor region (%) where a non-missing numeric test result is available for both the area of the CN tumor region and the relative area of moderately stained FAP in the CN tumor region.
 
This variable will be set to 0 if one or both are missing, 'NOT EVALUABLE' or 'NOT DIAGNOSTIC'.

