4	Measured Area of Strongly Stained FAP in the CN Tumor Region (μm^2)	
This is the back-calculated area of strongly stained FAP in the CN tumor region (strong positive) and will be calculated by multiplying the area of the CN tumor region (μm^2) and the relative area of strongly stained FAP in the CN tumor region (%) where a non-missing numeric test result is available for both the area of the CN tumor region and the relative area of strongly stained FAP in the CN tumor region.
 
This variable will be set to 0 if one or both are missing, 'NOT EVALUABLE' or 'NOT DIAGNOSTIC'.

5	Measured Area of Weakly Stained FAP in the IM Region (μm^2)	
This is the back-calculated area of weakly stained FAP in the IM region (weak FAP-positive) and will be calculated by multiplying the area of the IM region (μm^2) and the relative area of weakly stained FAP in the IM region (%) where a non-missing numeric test result is available for both the area of the IM region and the relative area of weakly stained FAP in the IM region.
 
This variable will be set to 0 if one or both are missing, 'NOT EVALUABLE' or 'NOT DIAGNOSTIC'.

Variable No.	FAP Derived Variable	Description and Calculation
6	Measured Area of Moderately Stained FAP in the IM Region (μm^2)	
This is the back-calculated area of moderately stained FAP in the IM region (moderate FAP-positive) and will be calculated by multiplying the area of the IM region (μm^2) and the relative area of moderately stained FAP in the IM region (%) where a non-missing numeric test result is available for both the area of the IM region and the relative area of moderately stained FAP in the IM region.
 
This variable will be set to 0 if one or both are 'NOT EVALUABLE' or 'NOT DIAGNOSTIC'.

7 ^[a]	Measured Area of Strongly Stained FAP in the IM Region (μm^2)	
This is the back-calculated area of strongly stained FAP in the IM region (strong FAP-positive) and will be calculated by multiplying the area of the IM region (μm^2) and the relative area of strongly stained FAP in the IM region (%) where a non-missing numeric test result is available for both the area of the IM region and the relative area of strongly stained FAP in the IM region.
 
This variable will be set to 0 if one or both are missing, 'NOT EVALUABLE' or 'NOT DIAGNOSTIC'.

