8 ^[a]	Total FAP-Positive Tumor Area (μm^2)	
This is the total FAP-positive area across the CN tumor region and the IM region (whole tumor) and will be calculated as the sum of component derived variables 2-7.
 
If all 6 component variables are 0 then this derived variable will be missing.

9 ^[a]	Total Measured Area of Weakly Stained FAP (μm^2)	
This is the total weak FAP-positive area across the CN tumor region and the IM region (whole tumor) and will be calculated as the sum of component FAP derived variables 2 and 5.

10 ^[a]	Total Measured Area of Moderately Stained FAP (μm^2)	
This is the total moderate FAP-positive area across the CN tumor region and the IM region (whole tumor) and will be calculated as the sum of component FAP derived variables 3 and 6.

11 ^[a]	Total Measured Area of Strongly Stained FAP (μm^2)	
This is the total strong FAP-positive area across the CN tumor region and the IM region (whole tumor) and will be calculated as the sum of component FAP derived variables 4 and 7.

12 ^[a]	Total Relative Area of Weakly Stained FAP (%)	
This is the percentage of weak FAP expression across the CN tumor region and IM region (whole tumor) and will be calculated using component FAP derived variables 1 and 9 as

Variable No.	FAP Derived Variable	Description and Calculation
		
(Total Measured Area Of Weakly Stained FAP / Total Analyzed Tumor Area) x 100
 
If the total analyzed tumor area is missing then this variable cannot be calculated and will be missing.

13 ^[a]	Total Relative Area of Moderately Stained FAP (%)	
This is the percentage of moderate FAP expression across the CN tumor region and IM region (whole tumor) and will be calculated using component FAP derived variables 1 and 10 as
 
(Total Measured Area Of Moderately Stained FAP / Total Analyzed Tumor Area) x 100
 
If the total analyzed tumor area is missing then this variable cannot be calculated and will be missing.

14 ^[a]	Total Relative Area of Strongly Stained FAP (%)	
This is the percentage of strong FAP expression across the CN tumor region and IM region (whole tumor) and will be calculated using component FAP derived variables 1 and 11 as
 
(Total Measured Area Of Strongly Stained FAP / Total Analyzed Tumor Area) x 100
 
If the total analyzed tumor area is missing then this variable cannot be calculated and will be missing.

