15 ^[a]	Total Relative FAP-Positive Tumor Area (TPS) (%)	
This is the total proportion score which is the percentage of FAP-positive area across the CN tumor region and the IM region (whole tumor) and will be calculated using component derived variables 1 and 8 as
 
(Total FAP-Positive Tumor Area / Total Analyzed Tumor Area) x 100
 
If the total analyzed tumor area is missing then this variable cannot be calculated and will be missing.

16 ^[a]	Total FAP Histoscore	
This is a histoscore for the combined CN tumor region and IM region (whole tumor) and will be calculated as a weighted score based on component derived variables 12, 13 and 14 as
 
(1 x Total Relative Area of Weakly Stained FAP) + (2 x Total Relative Area of Moderately Stained FAP) + (3 x Total Relative Area of Strongly Stained FAP).

CN=cancer; FAP=fibroblast activation protein, IM=invasive margin, TPS=total proportion score.

[a] Included in the listing of FAP test results.

The derived variables containing the [a] flag in [Table 9-1](#) above will be listed together with information on staining artifacts and any assay-specific comments provided by the laboratory.

Further informal analyses may be performed to explore the relationship between the PD and biomarker endpoints with antitumor activity, ADA status, and also with key PK parameters. The PK-PD effects of UCB6114 may be assessed using a population analysis approach. These analyses will also be performed separately outside of the CSR and the details of analysis methods will be included in a separate analysis plan.

The incidence of available historical tumor biopsies will be summarized by treatment group. The incidence of PD samples taken from blood and urine will be summarized by cycle and treatment group.

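### Table 9-1 codes unread FAP staining as 0 and a measured all-zero result as missing, so with numeric region areas the two give the same listed values

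*SAP*

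**What the plan says.** Table 9-1 in Section 9.2 is the same in the Part B and Part C plans. Its rules on missing values are:

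- **Variables 2 to 5 and 7** (stained area by region and intensity): "This variable will be set to 0 if one or both are missing, 'NOT EVALUABLE' or 'NOT DIAGNOSTIC".
- **Variable 6** (moderate staining, IM region): "This variable will be set to 0 if one or both are 'NOT EVALUABLE' or 'NOT DIAGNOSTIC". Unlike the other five, it does not mention missing inputs.
- **Variable 8** (total FAP-positive area, the sum of 2 to 7): "If all 6 component variables are 0 then this derived variable will be missing".
- **Variable 9** (total weak area): "will be calculated as the sum of component FAP derived variables 2 and 5". Variables 10 and 11 are built the same way. None of the three has a rule for missing values.
- **Variables 12 to 15** (percentages by intensity, and TPS): "If the total analyzed tumor area is missing then this variable cannot be calculated and will be missing". No other trigger is given.
- **Variable 1** (total analyzed area): "This variable will be missing if both the areas of the CN tumor region and IM region are missing, or if one or both are"; the sentence ends by naming the two codes for an unreadable result. It depends on the region areas and not on the staining. An IM area that is not applicable or missing is counted as 0.
- **Variable 16** (histoscore): a weighted sum of variables 12 to 14, with no missing rule of its own.

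Variables 1 and 7 to 16 are flagged for the FAP listing, which also carries notes on artifacts and laboratory comments.

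**The concern.** A tumor without FAP and a tumor whose FAP could not be read are different findings, and a derivation should keep them apart. Here a result that was not obtained enters as 0, and a later rule turns a full set of zeros into missing without asking where they came from. The rule on variable 8 looks like an attempt to restore the missingness that the zero coding removed, but it cannot do so and is not carried to variables 9 to 11.

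Elsewhere in Section 9.2 the plan handles the same problem differently. A Ki67 result that is not evaluable or missing becomes a separate category, and the Gremlin-1 histoscore is missing when there are no test results. Section 13.2 says the derived biopsy variables were added to make the laboratory results easier to interpret. At stake is whether the FAP listing can be read correctly, and whether any later exploratory use starts from sound values.

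**Working it through.** The plan states no figure on this point, so there is none to reproduce. The check applies the printed rules to a few cases.

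**Inputs.** The rules come from Table 9-1. The region areas (CN 1000 um2, IM 200 um2) and the staining percentages are illustrative assumptions; the documents give none. The result for cases A and B does not depend on them.

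**Formulas**, reading a percentage as a fraction:

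- Variables 2 to 7 = region area × relative stained area / 100, or 0 if unread.
- Variable 8 = sum of variables 2 to 7, or missing if all are 0.
- Variables 9, 10, 11 = 2+5, 3+6, 4+7.
- Variables 12 to 14 = 100 × (9, 10, 11) / variable 1.
- TPS (15) = 100 × variable 8 / variable 1.
- Histoscore (16) = 1 × var. 12 + 2 × var. 13 + 3 × var. 14.

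**Results**

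| Case | Var. 1 | Var. 8 | Var. 9–11 | Var. 12–14 | TPS | Histoscore |
|---|---|---|---|---|---|---|
| A. All staining measured as 0% | 1200 | missing | 0, 0, 0 | 0%, 0%, 0% | missing | 0 |
| B. Areas numeric, all staining not evaluable | 1200 | missing | 0, 0, 0 | 0%, 0%, 0% | missing | 0 |
| C. Areas and staining not evaluable | missing | missing | 0, 0, 0 | missing | missing | missing |
| D. CN 20/10/10%, IM staining not evaluable | 1200 | 400 | 200, 100, 100 | 16.7%, 8.3%, 8.3% | 33.3% | 58.3 |
| E. CN staining not evaluable, IM 20/10/10% | 1200 | 80 | 40, 20, 20 | 3.3%, 1.7%, 1.7% | 6.7% | 11.7 |

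**A against B.** All 16 variables agree. For A, variable 8 and TPS should be 0. For B, variables 8 to 16 should all be missing, so the zeros in 9 to 14 and 16 are wrong. Both rows also contradict themselves: TPS is missing while its weak, moderate and strong parts are each listed as 0%.

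**Limit of A against B.** The match is exact as printed when staining is not evaluable or not diagnostic. If IM staining is simply missing, the text does not say what variable 6 becomes; treated like the other five, it gives row B again.

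**C.** Unreadable areas make variable 1 missing, and variables 12 to 16 follow. This sample can be told from A, although variables 9 to 11 still show 0.

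**D and E.** The unread region's area stays in the denominator with no stain. In D, TPS = 100 × 400/1200 = 33.3%, against 100 × 400/1000 = 40% in the evaluable region; the histoscore is 58.3 against 20 + 2×10 + 3×10 = 70. In E, TPS = 100 × 80/1200 = 6.7%, against 100 × 80/200 = 40%. The listed value equals the evaluable-region value times that region's share of the area (1000/1200 in D, 200/1200 in E), so the size of the understatement depends on the split.

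**The case against.** The strongest reply is that little depends on these variables. Section 9.2 says the biopsy results are listed without summaries. Any analysis against antitumor activity is optional, sits outside the CSR and has its own analysis plan. Variable 1 also protects against the case where the areas cannot be read, and Section 9.2 says in general terms that FAP test results are listed by variable and sample, so a reader might recover the truth from the raw values or laboratory comments. For a tumor with no IM region, coding variables 5 and 7 as 0 is correct.

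Most of this stands, and it limits the consequence. It does not remove the defect. The FAP-specific text names the flagged derived variables, artifacts and comments, but not the raw percentages, so what the listing will show is unclear. Raw values beside them would not make the derived values right.

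Three stronger readings are tempting but not supported:

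- A reader might infer that every non-evaluable sample looks like a negative one. Case C shows otherwise: full agreement needs numeric areas, and the plan does not say how often those occur with unread staining.
- A reader might infer that all the listed values are wrong. Each profile is wrong only in part: a missing variable 8 and TPS is right for the unread sample, and zeros in 9 to 14 and 16 are right for the negative tumor.
- A reader might infer that multiplying an area by a percentage and later by 100 inflates results 100-fold. A percentage is ordinarily taken as a fraction, and variables 2 to 7 are labelled as areas in um2, so this is notation at most.

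**Conclusion.** The point holds in limited form. With numeric region areas, Table 9-1 gives a truly FAP-negative tumor and a sample with unread staining the same self-contradictory listing; this follows from the printed rules without any assumed number. When only one region is unread, FAP is understated. The amount rests entirely on assumed areas and staining: TPS of 33.3% or 6.7% in the two examples, against 40% in the evaluable region. These figures show the direction and the dependence on the split; they are not an estimate for this trial.

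No safety, dose-escalation or response endpoint is affected. It is still worth correcting, because a stated rule produces wrong listed values and the change is small.

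**What to change.** In Table 9-1 of both Parts:

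1. Set variables 2 to 7 to missing when the region exists but its area or staining result is missing, not evaluable or not diagnostic.
2. Set variables 5 to 7 to 0 when no IM region is defined, meaning an IM area of 0, not applicable or missing. This matches variable 1. Without it, propagating missing values would blank variables 8 to 16 for valid CN-only tumors.
3. Keep a measured 0% as 0.
4. Let missing values propagate to the dependent variables among 8 to 16.
5. Delete the all-zero rule on variable 8.
6. Give variable 6 the same wording as the other components.

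Case A then gives 0 for variables 8 to 14, TPS and histoscore, and case B gives missing for variables 8 to 16. Cases D and E also become missing for the whole-tumor variables; the 40% above is a benchmark, not what would be listed.

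The cost is a few lines of wording in each plan and a small change to the FAP derivations and their listing. No new data are needed.
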